## 2 Statistical methods

### 2.1 Data analysis general information

All analyses will be performed by Novartis or a designated CRO. The most recent version of SAS available in the statistical programming environment will be used for the analysis. The computations with respect to dose-response relationship will be developed and/or validated utilizing the most recent R programming under internally validated systems and environment. Dose-response will be tested and estimated with the MCP-Mod framework implemented in the {DoseFinding} package.

Categorical data will be summarized as frequencies and percentages. For continuous data, mean, standard deviation, median, 25th and 75th percentiles, minimum, and maximum will be presented.

CCI

#### Unscheduled assessments

The following points summarize the rule for unscheduled assessments:

- **Baseline:** All unscheduled assessments before the first dose should be included for consideration when calculating the baseline value
- For summary tables by visits, unscheduled assessments should not be included unless they qualify as baseline
- For shift tables, tables of abnormal values, and tables of worse post baseline all unscheduled assessments are included.

Unscheduled assessments will be reported with the scheduled assessments in the listings.

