#### **16.4.3 Dosing Schedule**

No.	Peanut Protein/Placebo (mg)	Cumulative Dose (mg)
1	1	1
2	3	4
3	10	14
4	30	44
5	100	144
6	300	444
7	600	1044
8	1000	2044
9	3000	5044

After each administered dose of allergen (or placebo) participants are to be monitored for any reaction. In the presence of an allergic reaction, and at the investigator's discretion, the interval between escalating doses can be increased or the challenge can be stopped. ([Section 16.4.5](#)).

The minimum observation time between doses is 15 minutes, the maximum observation time is 30 minutes. If needed, an additional 30 minutes of observation is permitted for further evaluation of symptoms. If continuation of the DBPCFC is still in question after 1 hour of observation, the challenge should be considered positive and should be stopped.

During and up to at least one hour after the completion of the DBPCFC, vital signs should be monitored at minimum:

- Start of challenge
- End of challenge
- With administration of epinephrine or any rescue medications
- Vital signs should be taken every 15 minutes after dosing for up to at minimum 1 hour after last dose of rescue medication(s)
- At any time deemed clinically necessary or relevant

Additionally, the participant should be, at minimum, observed every 15 minutes by a study team member after the last dose is given for signs and symptoms of reaction as well as AEs. These observation findings should be documented in source documents.

In the event of an allergen dosing error, the site should contact Novartis.

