## 2.7 Safety analyses

For all safety analyses, the safety set will be used. All listings will be presented by treatment group and tables will be presented by treatment arm and overall. For the 3 weeks Placebo followed by remibrutinib CCI for 1 week arm, the AEs will be listed by the placebo period and remibrutinib period separately to differentiate the AEs that occurred during the respective period.

Safety summaries (tables, figures) will include only data from the on-treatment period with the exception of baseline data from Screening Visits 1, 2 and 3 which will also be summarized where appropriate (e.g. change from screening summaries). In addition, a separate summary for death including on treatment and post treatment deaths will be provided. In particular, summary tables for AEs will summarize only on-treatment events, with a start date during the on-treatment period.

The on-treatment period lasts from the date of first administration of study treatment (Day 1) to 28 days after the end of treatment.

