### 2.7.1 Adverse events (AEs)

All AEs summarized will be displayed by treatment group and overall. All AEs listings will be presented by treatment arm and participant.

All events that the investigator classifies as reactions associated to the DBPCFC or SPT must be captured on the designated eCRF and will not be reported on the AE eCRF. These events will be reported separately and not included in reporting of treatment-emergent AEs (events started after the first dose of study medication or events present prior to start of treatment but increased in severity based on preferred term).

The number (and percentage) of participants with treatment emergent AEs will be summarized in the following ways:

1. by treatment, primary system organ class and preferred term
2. by treatment, primary system organ class, preferred term and maximum severity
3. by treatment, Standardized MedDRA Query (SMQ) and preferred term

Separate summaries will be provided for study medication related AEs, death, serious adverse events (SAEs), and other significant AEs leading to discontinuation. In case of sparse events in any of these categories occur, only a listing will be provided if deemed adequate.

A participant with multiple AEs within a primary system organ class is only counted once towards the total of the primary system organ class.

For the legal requirements of clinicaltrials.gov, two required tables on treatment-emergent AEs which are not SAEs with an incidence greater than a certain threshold based on the final database and on treatment-emergent SAEs and SAEs suspected to be related to study treatment will be provided by system organ class and PT on the safety set population.

If for a same patient, several consecutive AEs (irrespective of study treatment causality, seriousness and severity) occurred with the same SOC and PT:

- a. a single occurrence will be counted if there is  $\leq 1$  day gap between the end date of the preceding AE and the start date of the consecutive AE
- b. more than one occurrence will be counted if there is  $> 1$  day gap between the end date of the preceding AE and the start date of the consecutive AE

For occurrence, the presence of at least one SAE / SAE suspected to be related to study treatment / non SAE has to be checked in a block e.g., among AE's in a  $\leq 1$  day gap block, if at least one SAE is occurring, then one occurrence is calculated for that SAE.

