### 2.7.4.2 Vital signs

All vital signs data will be listed by treatment group, participant, and visit/time and, if ranges are available, abnormalities ([Table 2-7](#)) (and relevant orthostatic changes) will be flagged. Summary statistics and graphical presentations (e.g. boxplots) will be provided by treatment and visit/time.

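### The SAP keeps food-challenge reactions out of the adverse-event tables but has no matching rule for vital signs taken during the challenge and after rescue

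*SAP*

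**What the plan says.** **Unscheduled values.** SAP 2.1 states: "For shift tables, tables of abnormal values, and tables of worse post baseline all unscheduled assessments are included". It treats by-visit tables differently: "For summary tables by visits, unscheduled assessments should not be included unless they qualify as baseline". Neither rule mentions readings taken during a food challenge.

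**Readings on challenge days.** Protocol 16.4.3 asks for vital signs at the start and end of each challenge, "With administration of epinephrine or any rescue medications", and then: "Vital signs should be taken every 15 minutes after dosing for up to at minimum 1 hour after last dose of rescue medication(s". Table 8-1 marks vital signs for the clinical database on Days 26 and 28, one mark per visit, with no separate entry for readings within the challenge.

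**Safety window.** SAP 2.7: "The on-treatment period lasts from the date of first administration of study treatment (Day 1) to 28 days after the end of treatment". Both end-of-treatment challenge days fall inside it.

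**Adverse events.** For challenge and skin-prick reactions, SAP 2.7.1 says: "These events will be reported separately and not included in reporting of treatment-emergent AEs".

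**Vital-sign outputs.** SAP 2.7.4.2: "All vital signs data will be listed by treatment group, participant, and visit/time", with abnormalities flagged against Table 2-7. It continues: "Summary statistics and graphical presentations (e.g. boxplots) will be provided by treatment and visit/time". Table 2-7 sets notable limits (for example systolic pressure below 90 or at least 140, pulse below 50 or above 100) under a heading that speaks of cases newly occurring or worsening.

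**The concern.** The plan accepts that a reaction provoked by peanut protein is not a drug-safety event, but applies this only to adverse events. Clinically significant hypotension is a listed severe dose-limiting symptom in Protocol Table 16-6. Such a reaction would stay out of the treatment-emergent adverse events, while the blood pressure recorded during it could be flagged as notable under Table 2-7. A raised pulse after epinephrine would be handled the same way.

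Two mechanisms are at work. First, readings taken during a reaction or after rescue reflect the allergen and the rescue drug. Second, rescue triggers extra readings, so the number of chances to cross a limit can depend on the efficacy outcome. If remibrutinib protects, both would tend to put more notable values on placebo. Vital signs are part of a secondary safety endpoint, and this imbalance could hide a real effect on blood pressure or pulse.

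**Working it through.** The plan states no figure on this point, so there is none to reproduce. The check counts readings and then asks what the count alone could do.

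**1. Inputs from the documents**
- Post-baseline visits with vital signs (Table 8-1): Days 8, 22, 25, 26, 28 and 31, which is 6. The Day 26 and Day 28 values are taken as the start-of-challenge readings.
- Placebo arm: 72 × 1/8 = 9 randomized.
- Remibrutinib response at 600 mg or more: 80% (Amendment 02 rationale). The planned placebo rate is redacted. The unredacted historical rows in SAP Table 2-2 are 0/26 and 7/138, pooled 7/164 = 4.3%.
- The challenge runs to 3000 mg or the first dose-limiting symptom, so a 600 mg responder can still react later.

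**2. Minimum readings if the quarter-hour schedule follows the rescue dose**
- No rescue: 6 + 2 end-of-challenge readings = 8.
- Rescued on the peanut day: 8 + 1 at rescue + 4 quarter-hour readings = 13.

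**3. Effect of the count alone.** Assume a notable rate of 5% per reading, independent readings, and no effect of drug, allergen or epinephrine on the values.
- 8 readings: 1 − 0.95^8 = 33.7%.
- 13 readings: 1 − 0.95^13 = 48.7%.
- Placebo, 95% reacting and rescued: 0.95 × 48.7 + 0.05 × 33.7 = 47.9%.
- Active, 40% reacting and rescued: 0.40 × 48.7 + 0.60 × 33.7 = 39.7%.
- Gap: about 8 points. On 9 placebo participants, 0.08 × 9 is about 0.7 of a person.
- Equal shares reacting and rescued: gap zero.

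**4. Adding a reaction or epinephrine effect.** Assume 3% per ordinary reading, 10% for each of the 5 rescue-related readings, and 95.7% of placebo reacting. Without rescue the chance is 1 − 0.97^8 = 21.6%. With rescue it is 1 − 0.97^8 × 0.90^5 = 53.7%.

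| Share of reactors rescued | Placebo | Active, 20% react | Active, 60% react | Active, 95.7% react |
|---|---|---|---|---|
| 100% | 52% | 28% | 41% | 52% |
| 30% | 31% | 24% | 27% | 31% |

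With 1% to 5% per ordinary reading, rescue-related readings from that same rate up to 30%, and 30% to 100% of reactors rescued, the placebo excess runs from 0 to about 58 points. The documents do not locate the trial within that range.

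**5. Other reading of 16.4.3.** If the schedule follows each challenge dose, the four non-challenge visits give 4 readings and a completed nine-dose challenge day gives 1 + 9 = 10.
- Non-reactor: 4 + 10 + 10 = 24.
- Reactor at dose k with rescue: 4 + (1 + k + 5) + 10 = 20 + k, so 24 at dose 4 and 29 at dose 9.
- Reactor at dose 4 without rescue: 4 + (1 + 4) + 10 = 19.

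Early reactors are then not measured more often. Eligible participants reacted at 100 mg (dose 5) or less at screening, so most placebo reactions would be expected to be early.

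**6. After the fix.** With only the 6 scheduled readings in every arm, the chance at 5% per reading is 1 − 0.95^6 = 26.5% in all arms when the drug does not affect vital signs.

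**The case against.** The strongest objection is that SAP 2.7.4.2 names no shift, worst-value or notable-count table for vital signs. It names a flagged listing and by-visit statistics and boxplots, and SAP 2.1 already keeps unscheduled values out of by-visit tables. Where the SAP wants counts it says so, as for laboratory data (2.7.3) and ECG (2.7.4.1). Nor does either document say that within-challenge readings are entered in the database or count as unscheduled. This stands, so a reader should not infer that the contamination is certain. A count is implied only by the heading of Table 2-7. However, classification does not remove the problem. If the readings are unscheduled, the all-inclusive rule covers any notable-value output. If they are scheduled, nothing bars them from the by-visit statistics, and 2.7.4.2 gives no rule for several readings in one visit. Only source-only capture avoids it.

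A reader might also infer that reactors are measured far more often. That holds only for rescued reactors under the rescue-dose reading of 16.4.3, and rescue is not needed for a positive challenge (16.4.6). Under the challenge-dose reading the count imbalance disappears for early reactors, although reaction and epinephrine effects remain.

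A third tempting inference is that placebo would look worse with no drug effect at all. It would not: without an efficacy effect, reactor shares are equal in expectation and so is the table. The correct condition is no drug effect on vital signs.

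Finally, study drug is taken before the challenge, so excluding challenge-time readings moves some post-dose values out of the main outputs. This is a real cost, but those values are still shown by arm in the separate table, and Days 8, 22, 25 and 31 are untouched.

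**Conclusion.** The gap in the SAP is real but minor. The rule on unscheduled values has no challenge exception, the separation of challenge reactions covers adverse events only, and event-triggered readings fall within the on-treatment period. If those readings are captured, allergen and epinephrine effects can enter the flagged listing and any notable-value output built on Table 2-7. If remibrutinib reduces reactions, the likely direction is more notable values on placebo.

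The illustrative 8-point gap rests on the rescue-dose reading of 16.4.3 and on assumed values for the 5% rate, independence, and the 95% and 40% reacting and rescued; the documents give no rescue rate. Positive correlation between a person's readings would shrink the gap, and reaction or epinephrine effects would widen it. Severity is minor because the outputs are descriptive, with no test or decision rule, and about 9 placebo participants make any count imprecise.

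**What to change.** In SAP 2.1 and 2.7.4.2, state that:
- vital signs from the first challenge dose to discharge on challenge days are excluded from the by-visit, notable-value and worst-value drug-safety outputs;
- the pre-challenge reading is the Day 26 and Day 28 value (Protocol Section 8 already prefers vital signs before the challenge);
- challenge-time and post-rescue readings are shown by arm in a separate challenge table, in line with 2.7.1;
- within-challenge readings are or are not entered in the database.

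The cost is a short SAP addition, a time-based filter and one extra table. No new measurements are needed, but the filter requires time-stamped readings. Readings from first challenge dose to discharge on those two days would appear only in the separate table. Where a site keeps them in source only, the rule has no effect.

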## 2.1.1 General definitions

### 2.1.1.1 Study treatment

In this document, 'study medication', 'study treatment' or 'study drug' will be used to refer to investigational therapy assigned to a participant. Study drug refers to either remibrutinib or placebo.

The treatment arms in this study are as follows.

- Remibrutinib CCI
- Remibrutinib CCI
- Remibrutinib CCI
- Placebo for 3 weeks followed by remibrutinib CCI for 1 week
- Placebo

### 2.1.1.2 Study day

Study day will be defined as the number of days since the date of first dose of study drug. The date of first dose of study drug will be defined as Day 1 and the day before the first dose of study drug will be defined as Day -1.

Therefore, for a particular date, study day will be calculated as follows:

for dates on or after the first date of treatment,

$$\text{Study day} = \text{Assessment date} - \text{Date of first dose of study drug} + 1;$$

for dates prior to the first date of treatment,

$$\text{Study day} = \text{Assessment date} - \text{Date of first dose of study drug}.$$

### 2.1.1.3 Baseline definition

In general, baseline is defined as the last measurement taken before the first dose of study drug. Details on baseline calculations if different from this general definition will be provided in the later sections.

### 2.1.1.4 Post-baseline measurement

Post-baseline measurements are defined as those assessments after the first dose of study drug.

When change from baseline is of interest the following formula will be used for each scheduled visit and time-point where baseline and post-baseline values are both available:

$$\text{Change from baseline} = \text{post-baseline value} - \text{baseline value}.$$

If not stated otherwise for efficacy analyses, on-treatment values are defined as values taken post-baseline but no later than 1 day after last dose of treatment. Off-treatment values are defined as post-baseline values taken more than 1 day after last dose of treatment.

Details on calculation of post-baseline values are provided in the later sections.

If not stated otherwise, visit-windows will be used for the data that is summarized by visit; they are based on the study evaluation schedule and comprise a set of days around the nominal visit day. For any assessment, there are the protocol defined scheduled visits around which visit windows were created to cover the complete range of days within the study. When visit windows are used, all visits will be re-aligned, i.e., they will be mapped into one of the visit windows.

## 2.2 Analysis sets

For all analysis sets, participants will be analyzed according to the study treatment(s) received.

The safety set will include all participants who received at least one dose of the actual study drug (either remibrutinib or placebo) received though the actual treatment received does not match the randomized treatment. Safety set will be utilized for all safety summaries and analyses (Note: The wording “Safety set will be utilized for all safety/efficacy summaries and analyses” in Protocol v02 Section 12.1 is inconsistent with “PD population will be used for primary analysis” specified in Protocol v02 Section 12.4.2. To resolve the conflict, the PD analysis set instead of the Safety analysis set will be used for efficacy analysis).

The PK analysis set will include all participants with at least one available valid (i.e. not flagged for exclusion) PK concentration measurement, who received study drug (remibrutinib) and with no protocol deviations that impact on PK data.

The PD analysis set will include all participants with available PD data and no logistics/assay/analytical issues that may have impact on PD data.

The analysis sets and protocol deviation codes are related as follows:

Subjects without a signed informed consent obtained prior to participation in the study (INCL01) will be excluded from any analyses. All the protocol deviation codes and the details are included in [Table 2-1](#).

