### 1.2.1 Primary estimand(s)

The estimand is the precise description of the treatment effect and reflects strategies to address events occurring during trial conduct which could impact the interpretation of the trial results (e.g. premature discontinuation of treatment). The primary clinical question of interest is to understand the treatment effect of remibrutinib over placebo among participants who have completed actual DBPCFC after one month (4-5 weeks) of treatment and regardless of intake of rescue medication prior to actual DBPCFC at one month.

The primary estimand is described by the following attributes to address the primary clinical question of interest:

- Population:** Participants aged 18 – 55 years, inclusive, who have been diagnosed with IgE-mediated confirmed peanut allergy and met study inclusion/exclusion criteria and have undergone actual DBPCFC (2A & B) at one month (4-5 weeks).
- Variable:** Responder status defined as tolerating a single dose of  $\geq 600$  mg (1044 mg cumulative tolerated dose) of peanut protein without dose-limiting symptoms during the DBPCFC conducted at one month (4-5 weeks). The cumulative tolerated dose is the sum of the tolerated doses, not including the reactive dose. Dose-limiting symptoms indicate a true allergic reaction occurring during administration of a single dose of peanut protein at the

actual DBPCFC that should preclude the administration of any further doses in the view of the investigator.

- **Treatment:** The randomized treatment (one of five arms specified in [Section 2.1.1.1](#)) plus rescue medication (e.g., epinephrine, short-acting beta agonist, and/or anti-histamines) prior to actual DBPCFC at one month, if needed.
- **Intercurrent events:**
  - Discontinuation of treatment prior to the End of Treatment Assessments on Days 25, 26 and 28: Participants who discontinue treatment prior to actual DBPCFC, or who miss more than 20% of treatment doses throughout the study, or who miss medication doses for  $\geq 3$  consecutive days in the seven days prior to the one month actual DBPCFC part 2A due to any reasons other than adverse events
  - Intake of rescue medication prior to the actual DBPCFC
- **Summary measure:** Difference in the proportion of responders between remibrutinib and placebo

Supplementary estimands to the primary estimand are defined in [Section 2.5.5](#).

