**Table 2-1 Protocol deviation codes and analysis sets**

Category Deviation code	Text description of deviation	Data exclusion
Participants are excluded from specified analysis sets		
INCL01A	Signed informed consent not obtained	Exclude participants from all analysis sets
INCL06	Subjects not meeting positive DBPCFC at screening	Exclude participants from PD analysis set
OTH33	ICH-GCP non-compliance	Exclude participants belonging to these sites from PK analysis set and PD analysis set
EXCL07	Participant has current or previous history of a mast cell disorder, including macrocytosis or tryptase > or = 20 ng/ml	Exclude participants from PD analysis set
Participants are not excluded from analysis sets, but data being impacted by protocol deviation is treated as missing value:		

Category Deviation code	Text description of deviation	Data exclusion
TRT12	Each dose (peanut/pacebo) administration at DBPCFC was not separated by at least minimum of 15 minutes	DBPCFC results will be treated as missing values for efficacy analysis
OTH20	DBPCFC stopped though participant did not experience any Dose Limiting Symptoms	DBPCFC results will be treated as missing values for efficacy analysis
OTH24	The sequence of the amounts of 1 mg, 3 mg, 10 mg, 30 mg, 100 mg, 300 mg, 600 mg, 1000 mg, and 3000 mg of peanut protein and corresponding placebo was not followed at end-of-treatment DBPCFCs	DBPCFC results will be treated as missing values for efficacy analysis

Any updates to the above table will be updated via SAP amendment prior to final DBL as required.

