#### Primary endpoint – Responder rate

The statistical analysis will be based on the PD analysis set.

The null hypothesis of a no dose-response relationship for responder rate will be tested at a significance level of 10% against the one-sided alternative hypothesis of a dose-response relationship using the MCP-Mod methodology (Bretz et al 2005, Pinheiro et al 2014).

The primary endpoint will be analyzed based on logistic regression model, including treatment arm as a categorical variable (all remibrutinib doses and placebo) and including, but not limited to, log-transformed baseline total IgE and baseline tolerated peanut allergen dose as covariates. The logistic regression model is defined as follows. The response  $y_{ij}$  for subject  $i$  in dose group  $j$  receiving dose  $d_j$  is modelled as  $y_{ij} \sim \text{Bin}(1, p_{ij})$  with  $p_{ij} = \text{logit}^{-1}(\delta_j + x_{ij}^T \beta)$ , where  $x_{ij}$  are covariates of subject  $i$  in dose group  $j$ ,  $\delta_j$  are dose-specific intercepts and  $\beta$  are parameters associated with the covariates, common across dose groups. Any missing values in the covariates will be replaced with the median value for that variable. All covariates will be standardized to have a mean of 0 and a standard deviation of 0.5, so they are on the same scale as the binary input (Gelman, 2008).

In case of complete separation, the Maximum Likelihood estimate of the logistic regression does not exist. If this problem is encountered, we will replace the logistic regression by a Bayesian logistic regression with weakly informative priors. The Bayesian logistic regression model follows the same model equation as above, but incorporates weakly informative priors for the model's parameters. Priors are specified as follows: for parameters associated to the

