## 2.5.5 Supplementary analyses

In addition to completer analysis as the primary, the below estimands will be considered:

1. (Note: Given that the sample size has been largely reduced from 110 to 72, and responder rate to peanut protein is only measured at one single post-dose time point (i.e., at one month), supplementary estimands 1 and 3 that implement multiple imputation will not be performed. Supplementary estimand 1: Participants who do not undergo DBPCFC at one month, due to any reason [including operational complications caused by public health emergency (i.e., COVID-19)] other than AEs will be imputed under Missing at Random (MAR) assumption. The interest lies in the responder status after one month of treatment that would be observed if participants had not discontinued study due to reasons other than AEs before one month of treatment (hypothetical strategy).
2. Supplementary estimand 2: Composite strategy will be considered in addition to hypothetical strategy assuming any participant missing DBPCFC other than due to public health emergency (i.e., COVID-19) or participant missing doses >20% as non-responders.
3. Supplementary estimand 3: Treatment policy will also be considered to show the treatment effect in real-world conditions. Missing DBPCFC outcome in participants who discontinue remibrutinib or who miss more than 20% of study doses throughout the study treatment period or who miss doses  $\geq 3$  consecutive days in the 7 days prior to end-of-treatment visit on Day 26 for reasons other than adverse events before Part 2 DBPCFC visit will be imputed based on copy reference.
4. Supplementary estimand 4: to show treatment effect if treatment failure had not occurred, participants who had dose-limiting symptoms at any dose of the post-treatment blinded OFC to placebo will be considered as non-responders

Intake of rescue medication prior to DBPCFC conducted at end of study after one month of treatment: consider ignorable (treatment policy strategy, reflected in the treatment attribute) for all estimand strategies.

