## 5.6 Rule of exclusion criteria of analysis sets

**Table 5-2**      **Criteria leading to exclusion**

Analysis Set	Criteria that cause subjects to be excluded
Safety	Not randomized and/or no study drug taken/or no consent signed
PD	Not randomized and/or no study drug taken and/or no consent signed and/or ICH-GCP non-compliance and/or violation of key eligibility criteria

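### Efficacy is grouped by treatment received although the primary estimand uses the randomised arm, and SAP 2.2 and Table 5-2 disagree on who is in the efficacy set

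*SAP*

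**What the plan says.** **Grouping.** SAP 2.2 opens with a rule that has no exception for efficacy: "For all analysis sets, participants will be analyzed according to the study treatment(s) received". Protocol 12.1 has the same rule. The Treatment attribute of the primary estimand (SAP 1.2.1, and likewise Protocol 2.1) begins "The randomized treatment (one of five arms specified in" and goes on to rescue medication.

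**Which set carries efficacy.** SAP 2.2 notes that the protocol names two different sets for efficacy and settles the conflict: "the PD analysis set instead of the Safety analysis set will be used for efficacy analysis". SAP 2.5.2 repeats this for the primary endpoint: "The statistical analysis will be based on the PD analysis set".

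**Who is in that set.** There are two rules. SAP 2.2: "The PD analysis set will include all participants with available PD data and no logistics/assay/analytical issues that may have impact on PD data". SAP Table 5-2, which lists what excludes a participant from the PD set: "Not randomized and/or no study drug taken and/or no consent signed and/or ICH-GCP non-compliance and/or violation of key eligibility criteria". Neither document defines PD data. Table 2-1 adds that, for three deviations affecting the conduct of the food challenge (DBPCFC), "Participants are not excluded from analysis sets, but data being impacted by protocol deviation is treated as missing value".

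**Where dropouts are counted.** The primary analysis is restricted to completers (SAP 2.5.3). In SAP 2.5.5, supplementary estimands 1 and 3 are marked as not to be run. Supplementary estimand 2 works by "assuming any participant missing DBPCFC other than due to public health emergency" to be a non-responder, along with anyone who missed more than 20% of doses. It names no analysis set, so the general rule for efficacy applies.

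**The concern.** An estimand that compares randomised arms should be estimated with participants in their randomised arms. Treatment received is determined after randomisation, and grouping by it can break the comparability that randomisation provides. As-treated grouping is conventional for safety and PK. SAP 2.2 itself mentions a mismatch between actual and randomised treatment only when it defines the safety set.

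The conflict does not need a dispensing error to arise. In the 3-week-placebo arm, remibrutinib starts at Day 22. A participant in that arm who stops earlier has received only placebo. SAP 2.7 splits that arm into placebo and remibrutinib periods for adverse-event listings, but no rule says where such a participant belongs for efficacy.

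The second issue is set membership. A condition on data availability and assay quality suits laboratory biomarkers. If it also decides who enters the efficacy analyses, it can act on the wrong people. Supplementary estimand 2 is most exposed, because its purpose is to count participants who have no challenge result.

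**Working it through.** **1. The plan's own counts.** Inputs from Protocol 12.8: 72 participants, ratio 2:2:2:1:1, about 10% discontinuation.
- Arm sizes: 72 × 2/8 = 18 and 72 × 1/8 = 9.
- Completers: 18 × 0.90 = 16.2 and 9 × 0.90 = 8.1. The plan gives 14 to 16 and 7 to 8, so the upper ends reproduce. The lower ends imply 1 − 14/18 = 1 − 7/9 = 22% loss.
- Expected without a challenge, if every discontinuation costs the challenge: 0.10 × 72 = 7.2.

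**2. Grouping rule against estimand.** SAP 1.2.1 groups by randomised arm. SAP 2.2 groups by treatment received, in the set that 2.5.2 uses for the primary endpoint. The two agree only if nobody's treatment differs from assignment.

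**3. A 3-week-placebo participant who stops before Day 22.** Participants who discontinue treatment have no later challenge (Protocol 9.1.1), so this person is not in the primary analysis. In supplementary estimand 2 the person is a non-responder. If k of 9 placebo participants and r of 9 in the 1-week arm respond, as-treated grouping changes k/9 to k/10 and r/9 to r/8. For illustration, with k = 1 and r = 7:
- placebo: 11.1% to 10.0%
- 1-week arm: 77.8% to 87.5%

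At 10% discontinuation, 0.10 × 9 = 0.9 participants in that arm are expected to stop at any time, so typically at most one is affected. The 1-week arm is not in the dose-response fit, so there the change acts only through placebo.

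**4. The PD-set rules side by side.**

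| Rule applied | Participant with no challenge | Laboratory or logistics problem |
|---|---|---|
| 2.2, PD data means the challenge | Leaves the set, and so leaves estimand 2 | A laboratory assay problem has no bearing |
| 2.2, PD data means biomarker samples | Normally stays: samples are planned in all participants (Protocol 8.3), and early discontinuers should attend the End of Study visit (9.1.1), which collects peanut IgE and IgG4 (Table 8-1) | Could remove a valid challenge result |
| Table 5-2 | Stays | No effect |

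**5. Size of one participant.** Removing one responder from k/n changes the rate by (n − k)/[n(n − 1)]. Removing one non-responder changes it by k/[n(n − 1)]. The largest change that leaves the rate defined by others is 1/n.
- Only responder removed: 1/8 to 0/7 = 12.5 points; 1/7 to 0/6 = 14.3 points.
- Non-responder removed: 1/8 to 1/7 = 1.8 points; 0/8 to 0/7 = 0.
- Responder added: 0/8 to 1/9 = 11.1 points.

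**6. Size for supplementary estimand 2, first row of the table only.** Assume 80% response among active completers (the rate in Protocol Amendment 02). The planned placebo rate is redacted, so take p = 5% to 30%. Let a and b be the proportions without a challenge on active and placebo, with none due to a public health emergency.
- Set that drops them: 0.80 − p.
- Everyone, missing as non-response: 0.80(1 − a) − p(1 − b).
- Overstatement: 0.80a − pb.

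| Loss, active / placebo | p = 5% | p = 30% |
|---|---|---|
| 10% / 10% | 7.5 points | 5.0 points |
| 4 of 18 / 1 of 9 | 17.2 points | 14.4 points |
| 0 / 2 of 9 | −1.1 points | −6.7 points |

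The second row pairs the lowest planned active completion with the highest planned placebo completion, so it is an adverse case and not an expectation.

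**The case against.** The strongest reply is that Table 5-2 already supplies almost the set one would ask for: randomised, dosed and consented participants, less those with GCP non-compliance or a key eligibility violation. The SAP's document history lists sections 2.2 and 5.6 together when it clarifies that efficacy uses the PD set. Table 2-1 keeps participants in the sets when their challenge result is voided, so it separates membership from availability of a result. Even on the 2.2 wording, an eligible, dosed participant with no PD data of any kind is hard to construct. The two possible harms also need different meanings of PD data, so they should not be added together.

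That reply stands as far as it goes. A reader might infer that the plan removes dropouts from the composite analysis, or that it abandons the randomised comparison. The documents do not support either. Removal happens only if 2.2 overrides Table 5-2 and PD data means the challenge. Leaving out participants without a challenge also matches the primary estimand, whose stated population is those who underwent it. Nor is the PD set a new choice by the SAP, since Protocol 12.4.2 already named it for the primary analysis.

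On grouping, kits are assigned by medication number through the IRT, so wrong treatment may never occur. This limits the numerical effect but does not reconcile SAP 2.2 with SAP 1.2.1, and it does not cover the participant who stops before Day 22.

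**Conclusion.** Two textual conflicts remain. First, SAP 2.2 analyses efficacy by treatment received and the primary estimand specifies randomised treatment. This holds on any reading of the set definitions. Second, SAP 2.2 and Table 5-2 give different rules for who is in the efficacy set, and nothing says which prevails.

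The size is uncertain and may be nil. No mismatch rate is given. The 12 to 14 points for one placebo participant is a ceiling, and the usual shift is much smaller. For supplementary estimand 2, the overstatement of 5 to 7.5 points at equal 10% loss rests on 80% active response, an assumed placebo rate of 5% to 30%, and the reading in which participants without a challenge leave the set. Under Table 5-2 it is zero. The expected 7 of 72 is a count of missing challenges, not of participants lacking PD data. The documents give no figure for the latter.

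**What to change.** - State in SAP 2.2 that efficacy is analysed by randomised arm. This also settles where a 3-week-placebo participant who stops before Day 22 belongs.
- For efficacy, use the Table 5-2 rule: all randomised, dosed, consented participants, with the Table 2-1 exclusions (INCL01A, INCL06, EXCL07, OTH33), and no condition on PD-data availability or assay issues. Make 2.2 agree.
- Name the participants for each estimand: those with a challenge for the primary estimand, and everyone in the set for supplementary estimand 2.
- Keep the 2.2 data and assay filter for the biomarker analyses (IgE, IgG4, SPT), and as-treated analysis for safety and PK.

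The cost is SAP wording and one population flag. SAP 2.2 already provides for changing Table 2-1 by amendment before final database lock, so the same route is available. No data collection changes.
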